## **Table 10-2:** Highly Effective Methods of Contraception

- Combined (estrogen and progestogen containing) hormonal contraception associated with inhibition of ovulation (oral, intravaginal, or transdermal) in combination with a barrier method or/and an intrauterine device
- Progestogen-only hormonal contraception associated with inhibition of ovulation (oral, injectable, or implantable) in combination with a barrier method or/and an intrauterine device
- Intrauterine device
- Intrauterine hormone-releasing system^2
- Bilateral tubal occlusion
- Vasectomized partner
- Sexual abstinence
- Hormonal contraception may be susceptible to interaction with BNT411, which may reduce the efficacy of the contraception method. Therefore, hormonal contraception method alone is not considered as a highly effective method of contraception. Hormonal contraception should be combined with a barrier method or/and an intrauterine device to be a highly effective method of contraception.
- 2 Contraception methods that in the context of this guidance are considered to have low user dependency.
- Vasectomized partner is a highly effective birth control method provided that partner is the sole sexual partner of the woman of child-bearing potential (trial patient) and that the vasectomized partner has received medical assessment of the surgical success.
- In the context of this guidance sexual abstinence is considered a highly effective method only if defined as refraining from heterosexual intercourse during the entire period of risk associated with the trial treatments. The reliability of sexual abstinence needs to be evaluated in relation to the duration of the clinical trial and the preferred and usual lifestyle of the patient.

Table adapted from 'Recommendations related to contraception and pregnancy testing in clinical trials. Advisory non-binding guidance represented at the CTFG-meeting in Rome 2014' (MHRA 2014).

#### **Male Patients**

1. Recommendations for male patients with pregnant partner:

Male contraception (condom) is recommended in order to avoid exposure of an existing embryo/fetus. Contraception should be continued for 6 months after receiving the last dose of BNT411.

2. Recommendations for male patients with non-pregnant WOCBP partner:

The male patient should use condom during treatment and for 6 months after receiving the last dose of BNT411. For a non-pregnant WOCBP partner, contraception recommendations should also be considered.

All men must also not donate sperm during the trial and for 6 months after receiving the last dose of BNT411.

## 10.4.1 Collection of Pregnancy Information

Details will be collected of all pregnancies in female participants that occurred after the start of trial intervention and until 90 days after the last dose of BNT411. These details will be collected

after obtaining the necessary signed informed consent from pregnant participants (and if applicable their partners).

After obtaining the necessary signed informed consent from pregnant female partners directly, details will be collected of all pregnancies in female partners of male participants that occurred after the start of trial intervention and until 28 days after the last dose of BNT411. This applies only to male participants who receive BNT411.

The initial and follow-up information must be documented on the paper-based Pregnancy Reporting Form and **submitted to the sponsor within 24 hours** of learning of a participant's pregnancy/partner's pregnancy. The completed form needs to be sent to the Safety Report Fax number or Email detailed in Section 10.3.4. Completed pregnancy forms need to be signed by an investigator before faxing/mailing them to the sponsor. Blank reporting forms are provided to the investigator during the site initiation visit and are filed in the ISF.

The investigator will collect follow-up information on the subject/subject's partner and the neonate and the information will be forwarded to the sponsor. Pregnancy follow-up should describe the outcome of the pregnancy, including any voluntary or spontaneous termination, details of the birth, the presence or absence of any congenital abnormalities, birth defects, maternal or newborn complications and their presumed relation to the BNT411. Generally, the follow-up will be of a duration determined in consultation with the pediatrician.

While pregnancy itself is not considered to be an AE or SAE, any pregnancy complication or elective termination of a pregnancy will be reported as an AE or SAE. A spontaneous abortion is always considered to be an SAE and will be reported as such. Any post-trial pregnancy related SAE considered reasonably related to the trial intervention by the investigator will be reported to the sponsor. While the investigator is not obligated to actively seek this information in former trial subjects, he or she may learn of an SAE through spontaneous reporting.

# 10.5 Appendix 5: Response Evaluation Criteria in Solid Tumors Version 1.1 (RECIST 1.1)

## **Evaluation of Target Lesions**

- **Complete Response** Disappearance of all target lesions. Any pathological lymph nodes (whether target or non-target) must have reduction in short axis to <10 mm (the sum may not be "0" if there are target nodes).
- **Partial Response** At least a 30% decrease in the sum of the diameters of target lesions, taking as reference the baseline sum diameters.
- **Progressive Disease** At least a 20% increase in the sum of diameters of target lesions, taking as reference the smallest sum on trial (this includes the baseline sum if that is the smallest on trial). In addition to the relative increase of 20%, the sum must also demonstrate an absolute increase of at least 5 mm. (Note: the appearance of one or more new lesions is also considered progression.)
- **Stable Disease** Neither sufficient shrinkage to qualify for PR nor sufficient increase to qualify for progressive disease, taking as reference the smallest sum of diameters while on trial.

## **Evaluation of Non-Target Lesions**

- **Complete Response** Disappearance of all non-target lesions and normalization of tumor marker level. All lymph nodes must be non-pathological in size (<10 mm short axis).
- Non-complete response/Non-progressive disease Persistence of 1 or more non-target lesion(s) and/or maintenance of tumor marker level above the normal limits.
- **Progressive Disease** Unequivocal progression of existing non-target lesions will be defined as the overall level of substantial worsening in non-target disease such that, even in presence of SD or PR in target disease, the overall tumor burden has increased sufficiently to merit discontinuation of therapy (see Section 5.1). In the absence of measurable disease, change in non-measurable disease comparable in magnitude to the increase that would be required to declare progressive disease for measurable disease. Examples include an increase in a pleural effusion from 'trace' to 'large,' an increase in lymphangitic disease from localized to widespread.

## **Appearance of New Lesions**

The appearance of new lesions is considered progressive disease according to RECIST v1.1. Considering the unique response kinetics that have been observed with immunotherapy, new lesions may not represent true disease progression. In the absence of rapid clinical deterioration,

patients may continue to receive trial treatment if investigators consider that patients continue to benefit from treatment.

## **Evaluation of Overall Response**

For the overall response based on RECIST v1.1, confirmation of CR and PR is required by a repeat, consecutive assessment no less than 4 weeks from the date of first documentation. A confirmatory scan will also be required after an initial assessment of progressive disease for the purpose of managing treatment and in order to conduct the exploratory iRECIST analysis. If a patient discontinues the trial due to progressive disease and begins another treatment, a confirmatory scan is not required. If the next protocol-scheduled scan is due within 2 weeks after the confirmatory scan was obtained, the protocol-scheduled scan does not need to be done. Treatment of patients may continue between the initial assessment of progressive disease and confirmation of progressive disease (which is not required by RECIST v1.1). These patients may continue to receive trial therapy beyond confirmed progressive disease if investigators consider that patients continue to receive benefit from treatment. In the absence of clinical deterioration, such modifications to the RECIST may discourage the early discontinuation of treatment and provide a more complete evaluation of trial therapy anti-tumor activity than would be seen with conventional response criteria.

Table 10-3 provides overall responses for all possible combinations of tumor responses in target and non-target lesions with or without the appearance of new lesions.

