- 11 On-treatment imaging will be performed at Week 6 (+7 days), every 6 weeks (±7 days) for 48 weeks, and every 12 weeks (±7 days) thereafter until disease progression is assessed by the investigator (unless the investigator elects to continue treatment [see Section 8.5.1 for conditions of continued treatment]), withdrawal of consent, trial termination by the sponsor, or death, whichever occurs first, regardless of whether patients start a new anti-cancer therapy. Refer to Sections 10.5 and 10.6 of the protocol for RECIST 1.1. and iRECIST imaging and treatment guidelines.
- 12 ECOG status should be assessed before drug administration.
- 13 Adverse events (AEs) and serious adverse events (SAEs) should be reported from the time of signing the informed consent to 60 days (±7 days) after the patient receives the last dose of BNT411.
- 14 Suspected BNT411-related AEs only. Furthermore, in Germany only, all SAEs that occur in the patient throughout his or her lifetime should be reported refer to Table 1-5 and Section 10.3.4 for further details.
- 15 Patients who experience a delay in the administration of BNT411 should return to the clinic at least every 2 weeks (±3 days) and assessments listed under 'unscheduled visit' should be performed and reported in the eCRF. Unscheduled visit assessments should be performed at the investigator's discretion. For information on COVID-19 vaccination during the trial, see Section 10.9.
- 16 All labs at the screening visit must be obtained within 7 days of Cycle 1 Day 1. All lab assessments except for PK and biomarkers are done locally.
- 17 Laboratory samples should be obtained up to 3 days before treatment administration.
- 18 TSH, free-T3 and free-T4 will only be measured at screening, Cycle 1 Day 1, Cycle 2 Day 1, and on Day 1 of every evenly numbered cycle thereafter.
- 19 Serum pregnancy test is performed at screening. Thereafter, urine pregnancy test is sufficient unless indicated otherwise. The frequency of testing during treatment phase may depend on clinical indication per investigator's assessment and may also depend on local guidelines and regulations.

- 20 Medical history includes cancer history.
- 21 Prior/Concomitant Medications and Non-Drug Therapies include all anti-cancer pre-treatments.
- 22 Prior/Concomitant Medication and Non-Drug therapies only for BNT411 related AEs.

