# 7 Discontinuation of Trial Treatment and Patient Discontinuation/Withdrawal

#### 7.1 Discontinuation of Trial Treatment

Patients will receive BNT411 treatment until one of the predefined discontinuation of treatment criteria has been met:

- Radiographic disease progression per RECIST 1.1 (Section 8.5.1) or confirmed radiographic disease progression by iRECIST (if applicable),
- Death,
- Unacceptable AEs requiring BNT411 discontinuation (refer to Safety Stopping Criteria Section 6.6.5),
- Investigator believes that it is in the best interest of the patient to stop BNT411 treatment,
- Withdrawal of consent,
- Pregnancy
- Lost to follow-up

If BNT411 treatment is permanently discontinued for other reasons than radiographic disease progression, every effort should be made to continue tumor assessments.

Further information on discontinuation of atezolizumab, carboplatin and etoposide should be referred to the respective SmPC or USPI.

Patients should, whenever possible, irrespective of the reason for discontinuation, be examined as soon as possible and the treatment discontinuation visit should be performed (Section 8.3).

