## 7.2.2 Safety Follow-up Evaluations

Patients discontinuing from treatment for any reason will have safety follow-up visits 30 days ( $\pm 5$  days) and 60 days ( $\pm 7$  days) after the patient receives the last dose of BNT411. Separate safety follow-up visits should also be done after discontinuation of atezolizumab, carboplatin and etoposide, if it occurs  $\geq 21$  days later than BNT411. If the patient initiates new anti-cancer treatment within 60 days of the last dose of trial treatment, the safety follow-up visit should be performed prior to starting new anti-cancer treatment. Once new anti-cancer treatment is initiated, the patient will move into survival follow-up.

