## 8.5 Efficacy Assessments

## 8.5.1 Anti-tumor Activity Assessment – CT/MRI Imaging

Anti-tumor activity will be evaluated according to RECIST 1.1 (Eisenhauer et al, 2009) and iRECIST criteria (Seymour et al, 2017) (see Sections 10.5 and 10.6). Efficacy will be assessed by on-treatment imaging at Week 6 (+7 days), every 6 weeks (±7 days) for 48 weeks, and every 12 weeks (±7 days) thereafter until disease progression is assessed by the investigator (unless the investigator elects to continue treatment [see below]), withdrawal of consent, trial termination by the sponsor, or death, whichever occurs first, regardless of whether patients start a new anti-cancer therapy.

In all parts of the trial, treatment should be discontinued in all patients who exhibit evidence of progressive disease by RECIST 1.1. However, to better accommodate standard clinical practice which is guided by the fact that these patients have, in general, limited treatment options and such options have limited efficacy and significant toxicity, patients may be considered for treatment beyond progression at the discretion of the investigator and after appropriate discussion with the patient and obtaining informed consent, only if all of the following criteria are met:

- Absence of clinical symptoms or signs indicating clinically significant disease progression
- No decline in performance status
- Absence of rapid disease progression or threat to vital organs or critical anatomical sites [e.g. central nervous system (CNS) metastasis, respiratory failure due to tumor compression, spinal cord compression] requiring urgent alternative medical intervention
- No significant, unacceptable or irreversible toxicities related to trial treatment
- Patients must provide written consent to acknowledge deferring alternative treatment options including other clinical trials in favor of continuing trial treatment at the time of initial progression.

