Patients who continue treatment beyond radiographic disease progression per RECIST 1.1 should be closely monitored clinically and with a follow-up scan in 6 weeks or sooner if symptomatic deterioration occurs. Treatment should be discontinued if clinical deterioration due to disease progression occurs at any time, or if persistent disease growth is confirmed in a follow-up scan. In addition, patients should be discontinued for unacceptable toxicity or for any other signs or symptoms of deterioration attributed to disease progression as determined by the investigator after an integrated assessment of radiographic data and clinical status.

Patients who discontinue treatment for reasons other than radiographic disease progression (e.g. toxicity) will continue scheduled tumor assessments at the same frequency as would have been followed if the patient had remained on trial treatment.

Patients whose treatment schedule has been changed (e.g., delay due to toxicity) still should follow the original tumor assessment schedule (every 6 weeks [ $\pm 7$  days] for 48 weeks, and every 12 weeks [ $\pm 7$  days] thereafter).

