## Assessment and Decision at RECIST 1.1 Progression (Section 8.5.1)

For patients who show evidence of radiological PD by RECIST 1.1 as determined by the investigator, the investigator will decide whether to continue a patient on trial intervention until repeat imaging is obtained 4 to 8 weeks later (using iRECIST for patient management). This decision by the investigator should be based on the patient's overall clinical condition.

Any patient deemed clinically unstable should be discontinued from trial intervention at site-assessed first radiologic evidence of PD, and is not required to have repeat tumor imaging for confirmation of PD by iRECIST.

If the investigator decides to continue treatment, the patient may continue to receive trial intervention and the tumor assessment should be repeated 4 to 8 weeks later to confirm PD by iRECIST, per investigator assessment. Images should continue to be sent into the central imaging vendor for potential retrospective Blinded Independent Central Review (BICR).

Tumor flare may manifest as any factor causing radiographic progression per RECIST 1.1, including:

• Increase in the sum of diameters of target lesion(s) identified at baseline to ≥20% and ≥5 mm from nadir

Note: The iRECIST publication uses the terminology "sum of measurements," but "sum of diameters" will be used in this protocol.

- Unequivocal progression of nontarget lesion(s) identified at baseline
- Development of new lesion(s)

iRECIST defines new response categories, including immune unconfirmed progressive disease (iUPD) and immune confirmed progressive disease (iCPD). For purposes of iRECIST assessment, the first visit showing progression according to RECIST 1.1 will be assigned a visit (overall) response of iUPD, regardless of which factors caused the progression.

At this visit, target and nontarget lesions identified at baseline by RECIST 1.1 will be assessed as usual.

New lesions will be classified as measurable or non-measurable, using the same size thresholds and rules as for baseline lesion assessment in RECIST 1.1. From measurable new lesions, up to 5 lesions total (up to 2 per organ), may be selected as New Lesions – Target.

The sum of diameters of these lesions will be calculated and kept distinct from the sum of diameters for target lesions at baseline. All other new lesions will be followed qualitatively as New Lesions – Non-target.

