## **Management Following the Confirmatory Imaging**

If repeat imaging does not confirm PD per iRECIST, and the patient continues to be clinically stable, trial treatment may continue and follow the regular imaging schedule. If PD is confirmed, patients will be discontinued from trial treatment.

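### Protocol Appendix 5 lets treatment continue beyond confirmed progression where Appendix 6 requires it to stop, and asks for no re-check of criteria or renewed consent (minor)

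*Protocol*

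**What the plan says.** Four places in the protocol deal with treatment once progression has been confirmed on a follow-up scan.

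- **Appendix 5 (Section 10.5, Evaluation of Overall Response)** gives a permission: "These patients may continue to receive trial therapy beyond confirmed progressive disease if investigators consider that patients continue to receive benefit from treatment".
- **Appendix 6 (Section 10.6, Management Following the Confirmatory Imaging)** gives an instruction with no exception: "If PD is confirmed, patients will be discontinued from trial treatment".
- **Section 8.5.1** says that treatment of a patient continuing past RECIST 1.1 progression should end on clinical deterioration due to progression, "or if persistent disease growth is confirmed in a follow-up scan". It adds unacceptable toxicity and other signs of deterioration as reasons to stop.
- **Section 7.1** lists confirmed progression by iRECIST among the criteria for ending BNT411, qualified as applying where relevant.

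Section 8.5.1 also sets five criteria, all of which must hold, for any treatment beyond progression in any part of the trial. They are no clinically significant symptoms or signs of progression, no decline in performance status, no rapid progression or threat to vital organs, no unacceptable toxicity, and written consent to defer alternatives "in favor of continuing trial treatment at the time of initial progression".

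Footnote 11 to Tables 1-1 and 1-2 names Section 8.5.1 for the conditions of continued treatment, then adds: "Refer to Sections 10.5 and 10.6 of the protocol for RECIST 1.1. and iRECIST imaging and treatment guidelines".

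**The concern.** Take a patient whose progression has been confirmed and whom the investigator still believes to be benefiting. Appendix 5 lets the site keep dosing; Appendix 6 tells it to stop. Both stand in the current Version 6.0 text, and footnote 11 sends sites to both appendices for treatment guidance. No precedence clause says which appendix governs. Section 8 of the protocol allows no waivers or exemptions, and SAP Section 7.2 defines deviations as failures to adhere to protocol requirements. The same conduct is therefore permitted in one place and contrary to the protocol in another.

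What is at stake is whether a patient with confirmed progression may receive further doses of a first-in-human drug, and on what terms. The criteria are spelled out at initial progression. At confirmed progression, where the case for continuing is weaker, the Appendix 5 sentence names only the investigator's view of benefit and points to nothing else.

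**Working it through.** **Do the two appendices describe the same decision?** One might assign Appendix 5 to RECIST 1.1 and Appendix 6 to iRECIST. Appendix 5 rules this out. It notes that RECIST 1.1 does not require confirmation of progression, and it asks for the confirmatory scan so that treatment can be managed and the iRECIST analysis done. Both texts therefore act on the same scan.

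**The texts side by side, for a patient with confirmed progression and investigator-judged benefit:**

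| Place | Result | Strength |
|---|---|---|
| Appendix 5 | may continue | permission |
| Appendix 6 | will be discontinued | instruction, no exception |
| Section 8.5.1 | should stop if persistent growth is confirmed | narrower trigger than iCPD, which additional new lesions or a new progression factor can also satisfy |
| Section 7.1 | BNT411 ends | qualified as applicable |

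A site that stops complies with all four. A site that continues clearly departs from Appendix 6; whether it also departs from Sections 8.5.1 and 7.1 depends on the basis of confirmation and on the qualifier.

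**Size, for one patient.** The documents do not say how many patients are affected.

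Assumptions: nominal visit days, no delays, first progression at Week 6, and six more weeks (42 days) of treatment after confirmation. Appendix 6 gives the confirmation interval: "the tumor assessment should be repeated 4 to 8 weeks later to confirm PD by iRECIST". That puts confirmation at Week 10, 12 or 14. Section 8.5.1 asks for the follow-up scan in 6 weeks or sooner, so Week 14 fits only the Appendix 6 interval.

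Formulas: study day = 21 × (cycle − 1) + cycle day; scan day = 7 × week. BNT411 is given on Days 1, 8, 15 (Part 1A) or 2, 8, 15 (Part 1B) in Cycles 1–4, then on Day 1 or Day 2 of each cycle.

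| Confirmed at | Part 1A extra BNT411 days | Part 1B extra BNT411 days | Extra infusions |
|---|---|---|---|
| Week 10 (Day 70) | 71, 78, 85, 106 | 71, 78, 86, 107 | 4 |
| Week 12 (Day 84) | 85, 106 | 86, 107 | 2 |
| Week 14 (Day 98) | 106, 127 | 107, 128 | 2 |

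If first progression is at Week 12 and confirmation at Week 16, 18 or 20 (Days 112, 126, 140), the extra days are 127 and 148, 127 and 148, or 148 and 169 in Part 1A, and one day later each in Part 1B. That is 2 in every case. Four arises only when confirmation falls while dosing is still weekly.

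Shift in last trial dose, stopped versus continued, for first progression at Week 6:

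- Part 1A: 106 − 64 = 42, 106 − 78 = 28, 127 − 85 = 42 days.
- Part 1B: 107 − 66 = 41 (Day 66 is etoposide, Cycle 4 Day 3), 107 − 78 = 29, 128 − 86 = 42 days.

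The 60-day treatment-emergent window in protocol Section 9.4.2 and SAP Section 8.5.2 runs from the last trial dose, so it moves by the same 28–42 or 29–42 days. Scheduled safety follow-up can end sooner: "Once new anti-cancer treatment is initiated, the patient will move into survival follow-up".

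**The case against.** The strongest reply is that the gap is narrower than the Appendix 5 sentence suggests, and much of that stands.

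- **Safeguards.** A reader might infer that Appendix 5 allows dosing on investigator judgement alone. The documents do not support this. The lead-in to the Section 8.5.1 criteria covers treatment beyond progression generally; the reference to initial progression is only in the consent criterion. A patient can reach confirmed progression on treatment only by continuing past RECIST progression, so all five criteria, consent included, should already have been met. The Section 8.5.1 stops for clinical deterioration and unacceptable toxicity, and the safety stopping rules of Section 6.6.5, still apply.
- **Governing text.** A reader might also infer that nothing indicates where the stopping rule sits. Protocol Sections 4.1 and 6.1.2 and SAP Section 3.2 all refer to Section 7.1 for discontinuation, and footnote 11 names Section 8.5.1 for the conditions. This makes the Appendix 5 sentence the outlier, although no text expressly overrides it.
- **Breadth of the conflict.** It would be too strong to say that continuing breaches Sections 8.5.1 and 7.1 outright, given the narrower trigger in one and the qualifier in the other.
- **Permission only.** A site need not use it, and stopping satisfies every passage.

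None of this reconciles Appendix 5 with Appendix 6. Nor does it supply a renewed check: consent given to continue at first progression does not explicitly cover continuing once progression is confirmed. The mention in Appendix 5 of an absence of clinical deterioration explains the approach and is not set as a condition.

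**Conclusion.** The inconsistency is real and the text is wrong as written, but it is minor. Appendix 5 directly contradicts Appendix 6 and is out of line with Sections 8.5.1 and 7.1. What it lacks is any link to those sections, a re-check of the five criteria and a renewed consent at confirmed progression.

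Under the assumptions above, the consequence for one patient is about 2 extra BNT411 infusions over six weeks, or 4 if confirmation falls at Week 10. The six-week continuation is an assumption, and the documents do not show that any patient used the permission or is still on treatment.

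A reader might infer that trial results are compromised. They are not: DLT evaluation and escalation rest on Cycle 1 (protocol Sections 4.1.1.1 and 9.3), SAP Section 8.4 plans no efficacy analysis in Part 1, and the extra dosing is additional exposure and follow-up rather than bias. SAP Section 3 says that Part 2 is no longer applicable, so the issue reaches only patients still on Part 1 treatment.

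**What to change.** Delete the Appendix 5 sentence that permits therapy beyond confirmed progression. In the Appendix 5 paragraphs on new lesions and on overall response, refer to Sections 8.5.1 and 7.1 for the conditions of continuing and the criteria for stopping.

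If the sponsor does intend to allow continuation after confirmed progression, amend Appendix 6, Section 8.5.1 and Section 7.1 instead, allowing it only when the Section 8.5.1 criteria are met again and the patient gives renewed written consent.

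The first option costs one deleted sentence and the cross-references, with no new assessments or patients. Either option needs a protocol amendment with IRB/IEC approval (Section 10.1.1). The same amendment could align the persistent-growth trigger in Section 8.5.1 with the iCPD definition in Appendix 6, which the deletion alone leaves unmatched.
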